APPENDIX B. DETAILS OF STATISTICAL METHODOLOGY

Sample SAS Code for MMRM

```
proc mixed data= data;
  class trt01pn(ref='1') avisitn usubjid;
  model CHG = trt01pn base avisitn trt01pn *avisitn/ddfm=kr;
  repeated avisitn / subject= usubjid type=UN;
  lsmeans trt01pn*avisitn / diff=all cl alpha=0.05;
run;
```

Sample SAS Code for GEE

```
proc genmod data= data;
  class trt01pn(ref='1') avisitn usubjid;
  model AVALC = base trt01pn avisitn trt01pn *avisitn / dist=bin link=logit;
  repeated avisitn /subject= usubjid type=UN;
  lsmeans treatment*avisit / diff exp cl;
run;
```

Sample SAS Code for ANCOVA

```
proc mixed data= data;
  class trt01pn(ref='1');
  model CHG = trt01pn base / solution cl;
  lsmeans trt01pn / cl diff;
run;
```

Sample SAS Code for PMM-MI under MNAR

Step 1. Assessing the pattern of missing data

```
proc mi data=non_mono seed=xxx n impute=0;
  var trt01pn base y1-y3; *y1=Day 14, y2=Day 42, y3=Day 70;
  ods output misspattern=pattern;
run;
```

Step 2. Turning the arbitrary missing patterns to monotone missing patterns under MAR assumption

```
proc mi data=non_mono out=mono seed=xxx n impute=m
  min=.. x x x
  max=.. y y y; * period (.) means no imputation needed;
  var trt01pn base y1 y2 y3;
  mcimc chain=multiple impute=monotone;
run;
```

Step 3. Generation of imputed datasets for AVAL using control-based pattern imputation under MNAR

```
proc mi data=mono seed=xxx n impute=m out=imputed;
  min=. . x x x;
  max=. . y y y;
  by _imputation_;
  class trt01pn;
  var y1 y2 y3;
  monotone reg(/details);
  mnar model(y1 y2 y3/ modelobs=(trt01pn='1')); *only control group is used to derive
the imputation model;
run;
```

Step 4-1. Calculate CHG14, CHG42, and CHG70.

Step 4-2. Convert datasets into long format in which CHG variable represents all change from baseline with different values of avisit.

Step 5. Conducting model-based analysis using each imputed dataset

```
proc mixed data= imputed;
  by _imputation_;
  class subjid trt01pn(ref='1') avisitn;
  model chg = trt01pn base avisitn trt01pn*avisitn / ddfm=kenwardroger;
  repeated avisitn / subject=usubjid type=UN;
  lsmeans trt01pn*avisitn / diff=all cl alpha=0.05;
  ods output lsmeans=lsmeans diff=diffs;
run;
```

Step 6. Pooling the results from the imputed *m* datasets for inference

```
proc sort data=lsmeans;
  by trt01pn avisitn _imputatoin_;
run;

proc mianalyze parms=lsmeans;
  modeleffects estimate;
  ods output ParameterEstimates=lms;
  by treatment avisit;
run;

proc sort data=diffs;
  by avisit _imputatoin_;
run;

proc mianalyze parms=diffs;
```

```
modeleffects estimate;  
ods output ParameterEstimates=dif;  
by avisit;  
run;
```

Sample SAS Code for Tipping Point Analysis

```
/*-----*/  
/*--- Generate imputed data set for specified shift parameters ---*/  
/*--- data= input data set ---*/  
/*--- smin= min shift parameter ---*/  
/*--- smax= max shift parameter ---*/  
/*--- sinc= increment of the shift parameter ---*/  
/*--- out= output imputed data set ---*/  
/*-----*/  
%macro midata( data=, smin=, smax=, sinc=, out=);  
  data &out;  
  set _null_;  
run;  
  
/*----- # of shift values -----*/  
%let ncase= %sysevalf( (&smax-&smin)/&sinc, ceil );  
/*----- Imputed data for each shift -----*/  
%do jc=0 %to &ncase;  
  %let sj= %sysevalf( &smin + &jc * &sinc);  
  proc mi data=&data seed=xxx nimpute=m out=outmi;  
    class trt01pn;  
    monotone reg(y1 y2 y3);  
    mnar adjust( y1 y2 y3 / shift=&sj adjustobs=(trt01pn='1') ); *active treatment is used;  
    var trt01pn y1 y2 y3;  
  run;  
  
  data outmi;  
    set outmi;  
    Shift= &sj;  
  run;  
  
  data &out;  
    set &out outmi;  
  run;  
%end;  
%mend midata;
```

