8.3.3.3.1. Control-Based Pattern Mixture Model Multiple Imputation

If $\geq 10\%$ of participants have missing data in the primary endpoint, a sensitivity analysis using control-based Pattern Mixture Model Multiple Imputation (PMM-MI) under the missing not at random (MNAR) assumption will be used to investigate the impact of missing data (Lingling 2019, SAS Institute Inc.). MNAR assumes the missingness depends on the unobserved study data and cannot be predicted solely based on participant's observed data.

In cases where there is a missing baseline value, the missing baseline value will not be imputed with control-based PMM-MI. Instead, the average of all available baseline values (regardless of treatment group) will be populated for the missing baseline value. After this step, the control-based PMM-MI will be applied. Control-based PMM-MI under MNAR involves four steps as described below.

Step 1. Assessing the pattern of missing data.

To investigate the pattern of missing data, "ods output misspattern" will be used in the MI procedure of the SAS system (PROC MI). The imputation method will be based on the observed pattern of missing data and amount of missing data. The pattern of missing data will be assessed as monotone or arbitrary.

Step 2. Turning the arbitrary missing patterns to monotone missing patterns under missing at random (MAR) assumption.

If a mixture of non-monotone and monotone missing patterns exist in the data with majority of monotone missing patterns, then the arbitrary missing patterns will be converted to monotone missing patterns under MAR assumption.

Step 3. Generation of imputed datasets for AVAL using control-based pattern imputation under MNAR.

PROC MI will be used to generate m complete datasets. The selection of m depends on the required computing time and will be determined based on the amount of missing information prior to the last patient last visit but has been recommended varying from 5 to 100.

Step 4. Convert datasets into long format in which CHG variable represents all change from baseline with different values of avisit.

Step 5. Conducting model-based analysis using each imputed dataset.

The m complete datasets are analyzed using MMRM.

Step 6. Pooling the results from the imputed m datasets for inference.

The results from the m complete datasets are combined to produce inferential results.

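### When missing data are non-monotone, the SAP's control-based imputation code creates m × m data sets instead of the m to be pooled, and its MMRM step most likely stops

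*SAP*

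**What the plan says.** SAP 8.3.3.3.1 describes the control-based analysis in words. If non-monotone patterns occur among mainly monotone ones, Step 2 first fills the gaps under MAR so that the data become monotone. For Step 3, "PROC MI will be used to generate m complete datasets". For Step 5, "The m complete datasets are analyzed using MMRM". Step 6 pools those m results. The value of m is left open; the text says only that it "has been recommended varying from 5 to 100" and that it will be set from the amount of missing information before the last participant's last visit.

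SAP Appendix B gives the code (`n impute` is read here as `nimpute`, the space being taken as a text-extraction artefact):

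- Step 2: "proc mi data=non_mono out=mono seed=xxx n impute=m"
- Step 3: "proc mi data=mono seed=xxx n impute=m out=imputed", run with "by _imputation" as its grouping line
- Step 5: PROC MIXED, again grouped by the imputation index alone. Its REPEATED statement matches the one in the primary MMRM sample, "repeated avisitn / subject= usubjid type=UN".

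For the tipping-point analysis, the Appendix B macro imputes with "monotone reg(y1 y2 y3" in its MONOTONE statement. Neither the macro nor SAP 8.3.3.3.2 includes a step that makes the data monotone first. Section 8.3.3.3.2 fixes the number of imputed data sets at 100.

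**The concern.** In the two-stage approach the text describes, the first stage carries the m-fold replication and the second stage completes each of those sets once. The code replicates at both stages. It creates no second index, discards no draws and gives no combining rule for nested imputations, so the output of Step 3 is not what Steps 5 and 6 are built to receive.

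This is the first-listed check on how the primary result depends on missing data. SAP 8.3.3.3 commits the sponsor to explain any sensitivity result that points in a different direction from the primary one. If the code cannot deliver a valid result, the programmer must choose a repair that the SAP does not specify, and the possible repairs are not equivalent. For example, one draw in Step 2 and m in Step 3 would also yield m sets, but it would treat the filled-in intermittent values as known.

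**Working it through.** **1. The plan's own figure.** The text says m sets are generated, analysed and pooled, with m from 5 to 100. The code gives m (Step 2) × m (Step 3, within each Step 2 set) = m²:

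| m | Sets in the text | Sets from the code | Rows per participant-visit in each Step 5 fit |
|---|---|---|---|
| 5 | 5 | 5 × 5 = 25 | 5 |
| 20 | 20 | 20 × 20 = 400 | 20 |
| 50 | 50 | 50 × 50 = 2,500 | 50 |
| 100 | 100 | 100 × 100 = 10,000 | 100 |

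The stated figure is therefore not reproduced. With one imputation per group in Step 3, the count is m × 1 = m, with one row per participant and visit, and it agrees with the text.

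**2. What Step 5 receives.** The model has three post-baseline visits (Days 14, 42 and 70). If all 76 planned participants are included, a completed set has 76 × 3 = 228 rows. At m = 5, each Step 5 group has 228 × 5 = 1,140 rows carrying only 76 participant identifiers.

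**3. Copies recognised as the same participant.** Let Σ be the 3 × 3 visit covariance and J the m × m matrix of ones. Rows that share a participant and a visit share a covariance index, so the implied within-participant matrix is J ⊗ Σ, of size 3m and rank 1 × 3 = 3. At m = 5 it has rank 3 out of 15, so it is singular and the likelihood is undefined. The fallback structures in SAP 8.3.3.1 are also indexed by visit and do not remove the duplication. That sequence ends with no result being reported.

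**4. Copies treated as separate participants.** This needs a departure from the printed code or a particular reading of it: Step 5 lists `subjid` in CLASS but names `usubjid` as the subject. Each fit would then see m times the sample, and its standard error would shrink by about √m: √5 = 2.24 and √20 = 4.47. A simulation used 38 per arm, 20% dropout and three post-baseline visits, with an assumed correlation of 0.75 between visits. The ratio of the correct to the stacked pooled standard error was:

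| Intermittent missingness (assumed) | m = 5 | m = 20 |
|---|---|---|
| 0% | 2.24 | 4.55 |
| 5% | 2.16 | 3.79 |
| 15% | 2.05 | 3.18 |

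The 0% row is the case in which Step 2 is not needed. Where Step 2 does apply, the factor falls below √m, because the between-imputation variance from Step 2 survives.

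**5. Whether the analysis will be run.** The trigger is 10% of participants; 10% of 76 is 7.6, so 8 participants. The plan anticipates 20% dropout: 76 × 0.20 = 15.2, about 15. Missing primary endpoints could be fewer, since participants who stop treatment are asked to keep attending and early termination visits are mapped to analysis windows.

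**6. Tipping point.** A participant who misses Day 42 but attends Day 70 has a non-monotone pattern. Section 8.3.3.3.1 provides for this; Section 8.3.3.3.2 does not.

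**The case against.** The governing text has the count right. The code is labelled as a sample, and its placeholders for the seed, m and the range limits mean that it cannot run unedited. It has other slips that would force a rewrite, such as a misspelt sort variable and range limits placed after a closing semicolon in Step 3. A program that stops is noticed and repaired. Step 2 applies only to non-monotone data, the analysis only at 10% or more missing, and a complete-data analysis is planned on the same trigger.

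Most of this stands, and it limits the consequence. It does not remove the contradiction. Appendix B is the part of the SAP that details the methodology, and only there is a number of draws assigned to Step 2. Correcting the spelling and the semicolons would still leave m × m sets.

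A reader might infer something stronger: that the analysis will report standard errors √m too small, a factor of 10 at m = 100, and so make a fragile primary result look robust. The documents do not support that. As printed, the copies share a participant identifier and a visit, which points to a visible failure rather than a falsely tight interval.

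A reader might also take the lower end of the range for m as an error. It is not: the SAP ties m to the amount of missing information. Nor is it established that the tipping-point macro receives raw data, because its argument is described only as an input data set. What can be said is that no monotone step is specified.

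**Conclusion.** The point holds as a contradiction between SAP 8.3.3.3.1 and Appendix B whenever Step 2 is used: m² data sets against m. Followed as printed, the code gives no valid result, and the most likely outcome is that the MMRM stops. Too-small standard errors are a conditional risk only, by a factor of about 2.0 to 2.2 at m = 5 and 3.2 to 4.6 at m = 20 over 0–15% intermittent missingness. Those factors rest on the assumed correlation of 0.75 and on the copies being read as separate participants.

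SAS was not run. How PROC MI treats an imputation index already in use as the BY variable is an assumption, although keeping or overwriting it leaves m copies per index value either way. The primary MMRM is not affected. The tipping-point gap is a related omission that matters only if patterns are non-monotone.

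**What to change.** In Appendix B:

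- **Non-monotone patterns present:** keep `nimpute=m` in Step 2 and set `nimpute=1` in Step 3, run by the Step 2 imputation index. Steps 5 and 6 then receive m sets.
- **All patterns monotone:** skip Step 2, drop the BY line in Step 3 and keep `nimpute=m` there.
- **Tipping point, non-monotone patterns:** start the macro from the Step 2 monotone sets, by imputation index, with `nimpute=1`, and add the monotone step to SAP 8.3.3.3.2.

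Use one participant identifier throughout Step 5. Setting m = 100 for the control-based analysis, as the tipping-point section already does, would be a sensible alignment but is optional.

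The cost is a few lines of code and a sentence or two of SAP text before database lock. Nothing in the trial's conduct, data collection or primary analysis changes.

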8.3.3.3.2. Tipping Point Analysis

If $\geq 10\%$ of participants have missing data in the primary endpoint, another sensitivity analysis – tipping point analysis – will be considered to investigate the robustness of the result to departures from the MAR assumption of the MMRM model and to identify the tipping point

where the treatment effect in participants with missing data overturns the treatment effect from statistically significant to statistically non-significant.

Hence the tipping point analysis will only be performed if the primary efficacy analysis is statistically significant in treatment effect.

Implementing the tipping point approach includes the following steps ([Yuan 2014](#), [SAS Institute Inc.](#)):

Step 1. Missing baseline will be imputed as the mean of non-missing baseline for all other participants. For post-baseline, under the MNAR assumption, missing WAIS-IV Coding test score up to Day 70 will be imputed using PROC MI under MNAR.

Step 2. The imputed values for observations in SAGE-718 treatment group will be adjusted directly using the shift parameter (δ).

Step 3. The imputed datasets with the shift parameter applied will be analyzed using PROC MIXED.

Step 4. The results will be combined for the inference using PROC MIANALYZE.

Step 5. Step 1-4 will be repeated until the result is not statistically significant.

Step 6. If needed, step 1-5 will be repeated with more stringent shift parameter applied until the result is not statistically significant.

The shift parameter (δ) value will be progressively decreased, and process repeated until non-significant p-value is achieved. One hundred datasets will be generated.

The tipping point summary for each pairwise comparison will include LSM difference, the 95% CI, and p-value for each of δ value. Iterations including the tipping point will be summarized.

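### The control-based and tipping-point imputation code omits the baseline Coding score; unless visit correlations decay over time, this costs some precision and pulls the control-based estimate towards the Day 14 difference.

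*SAP*

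**What the plan says.** The treatment of baseline differs between parts of SAP Appendix B:

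- Control-based Step 1 (missing-data pattern) includes it: "var trt01pn base y1-y3; *y1=Day 14, y2=Day 42, y3=Day 70".
- Control-based Step 2 (making the pattern monotone) includes it: "var trt01pn base y1 y2 y3".
- Control-based Step 3 creates the control-based values, through "mnar model(y1 y2 y3/ modelobs=(trt01pn='1')); *only control group is used to derive". Its VAR statement lists only y1, y2 and y3.
- Control-based Step 5 (analysis of the imputed data) includes it: "model chg = trt01pn base avisitn trt01pn*avisitn / ddfm=kenwardroger".
- The tipping-point imputation leaves it out: "var trt01pn y1 y2 y3".

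The text does not restore it. SAP 8.3.3.3.1 and 8.3.3.3.2 name no imputation covariates. Both make baseline complete before any post-baseline score is imputed. The first says "the average of all available baseline values (regardless of treatment group) will be populated for the missing baseline value"; the second says "Missing baseline will be imputed as the mean of non-missing baseline for all other participants".

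Both analyses require at least 10% missing on the primary endpoint. The tipping point also requires a significant primary result.

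**The concern.** Raw Coding scores are imputed without the participant's own baseline. They are then turned into changes from that baseline and analysed with baseline as a covariate, so the imputation model is poorer than the analysis model. Two things can follow.

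1. **Precision.** Imputed values scatter more than they need to, and the pooled standard error grows.
2. **Control-based estimate.** Without baseline, the placebo-derived regression puts more weight on the Day 14 score. A SAGE-718 dropout then carries more of any Day 14 difference forward to Day 42, which weakens the control-based assumption that the analysis is meant to impose.

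For the tipping point, a result may look fragile at zero shift because a covariate was dropped and not because of any departure from missing at random. The five bound slots against three variables in Step 3 match the layout of Step 2, so the omission looks like a slip.

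**Working it through.** **Inputs from the SAP.** Section 5.2 gives a z-score difference of 0.8 with SD 1.07, so 0.8/1.07 = 0.748, stated as 0.75. With 30 per arm and two-sided 0.05, t-test power is 81.5%, consistent with the stated 80%. Then 60/0.8 = 75, or 38 per arm = 76. The plan's figures reproduce. On 76 participants the 10% trigger is 7.6, so 4 of 38 per arm (10.5%) just exceeds it. The planned 20% dropout is 7.6 per arm, so 8 of 38 (21.1%) is taken as the upper end.

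**Assumptions (not in the documents).** Equal correlation r = 0.7 to 0.9 between visits; dropout at random and equal between arms; Day 14 observed; a share f of the Day 42 effect already present at Day 14.

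**Weight on Day 14 in the placebo-only regression for Day 42.** Without baseline it is r; with baseline it is r/(1+r). At r = 0.8 these are 0.800 and 0.444. Residual variance is 1 − r² without baseline and 1 − 2r²/(1+r) with it: 0.360 and 0.289 at r = 0.8.

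**Control-based estimate**, with p the share missing:

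- without baseline: 0.75 × [(1 − p) + p·f·r]
- with baseline: 0.75 × [(1 − p) + p·f·r/(1+r)]

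At r = 0.8, in SDs of change:

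| Missing per arm | f | Without baseline | With baseline |
|---|---|---|---|
| 4 of 38 | 0.5 | 0.703 | 0.689 |
| 4 of 38 | 1 | 0.734 | 0.706 |
| 8 of 38 | 0.5 | 0.655 | 0.627 |
| 8 of 38 | 1 | 0.718 | 0.662 |

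The difference, as a share of the true effect, is p·f·r²/(1+r). With f = 0 it is zero. With f = 0.5 and r = 0.7 it is 0.105 × 0.5 × 0.288 = 1.5% (4 of 38) or 3.0% (8 of 38). With f = 1 and r = 0.9 it is 0.105 × 0.426 = 4.5% or 9.0%.

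**Standard errors by simulation.** The control-based runs used 1200 trials with 25 imputations per scenario, sequential Bayesian regression, Rubin pooling and a Day 42 ANCOVA with baseline. Leaving baseline out raised the pooled SE by 3 to 5% (4 of 38) and 5 to 8% (8 of 38). Simulated estimates agreed with the formulas within 0.01.

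**Tipping point at zero shift.** These runs used 700 trials with 100 imputations and half the effect at Day 14. The comparator was a fitted three-visit unstructured MMRM, with Kenward-Roger degrees of freedom approximated.

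| | 4 of 38, without / with | 8 of 38, without / with |
|---|---|---|
| SE above the MMRM's | 5–6% / 1% | 8–11% / 2% |
| Primary-significant trials non-significant at zero shift | 2–5% / 0–1% | 5–8% / 1–3% |
| RMS distance from MMRM estimate (SD) | 0.04 / 0.02 | 0.05–0.06 / 0.03 |

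The mean estimate was within 0.006 SD of the MMRM's either way. Monte Carlo error on the second row is about 1 point.

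**Second simulation** (600 trials, 20 imputations, 20% dropout, r = 0.8, f = 0.5). Control-based estimates were 0.414 and 0.396 score SD. Dividing by √(2 × 0.2) = 0.632 gives 0.655 and 0.626 SD of change, in line with the 8 of 38 row. With the full effect at Day 14 but harmful, the tilt reversed sign (−0.032 score SD). Under the null, with equal random dropout, there was no tilt, and control-based rejection was about 0.02 with or without baseline.

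**Decaying correlation.** If correlation is r per visit step, baseline and Day 42 correlate r². The partial weight on baseline is (r² − r·r)/(1 − r²) = 0, so baseline adds nothing once Day 14 is known. Partial decay lies between: with correlations 0.80 (baseline–Day 14), 0.75 (baseline–Day 42) and 0.80 (Day 14–Day 42), the Day 14 weight is 0.800 without baseline and 0.556 with it.

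**The case against.** **It is only sample code.** It has placeholders, and Step 3 would not run as printed: the bounds stand after the PROC MI statement has closed, with five slots for three variables. Debugging might expose the slip. SAP 8.3.3.3.1 also says that the method will depend on the pattern and amount of missing data. That stands as an explanation of how the slip arose. It does not restore baseline, because no text names the covariates, and the tipping-point list omits baseline without any such warning sign.

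**Few participants are exposed.** This stands and limits the reach. Participants who stop treatment should keep attending. Table 3 in SAP 8.3.2 counts a Coding score on Days 29 to 56 as Day 42, and early-termination visits are mapped to analysis visits. In the control-based analysis, Step 2 fills a missing Day 42 with baseline in the model when Day 70 is present. Most remaining dropouts should have a Day 14 score. If one dropout per arm had no post-baseline Coding score, the SE increase would be 5 to 20%, but the plan makes that case unlikely.

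**The effects are conditional and small.** This also stands. A reader might infer that the omission always favours SAGE-718. It does not: the pull is towards the observed Day 14 difference, vanishes without one, and reverses if the drug harms.

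**The promise in SAP 8.3.3.3 to explain discrepancies.** A reader might infer that the omission would produce the kind of discrepancy that section covers. For the control-based estimate it would not. That section concerns a result in a different direction from the primary. Leaving baseline out moves the mean estimate closer to the true 0.75 (0.703 against 0.689), and shifts of 0.014 to 0.056 SD would not plausibly reverse the sign.

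**The tipping-point error works against the sponsor.** True: the result can look more fragile than it is. It is still an artefact.

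**Conclusion.** The omission is plain in the code and is a minor defect. If the analyses run and correlations do not simply decay, control-based SEs rise by roughly 3 to 8%. Zero-shift tipping-point SEs lie about 5 to 11% above the MMRM's, against 1 to 2% with baseline. The control-based estimate moves by between 0% and about 4.5% (4 of 38) or 9% (8 of 38) of the true effect. With a Day 14 benefit, the control-based analysis is slightly less conservative than intended. The zero-shift tipping-point estimate is not biased on average under dropout at random.

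Confidence that baseline is missing is high; confidence in the sizes is moderate, because the correlations, the Day 14 effect and the dropout pattern are assumed. Dropout that depends on baseline differently by arm could move both estimates further. One stress case, with about 10% and 30% dropout in the two arms, moved them by 0.069 (control-based) and 0.020 (tipping point) score SD on a true 0.474. Nothing in the documents points to such dropout, so no size is claimed for it.

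A reader might also infer a threat to the primary result or to type I error. The primary MMRM uses neither imputation and contains baseline, and the null simulations showed no inflation.

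**What to change.** Before database lock:

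- **Control-based Step 3:** use `var base y1 y2 y3;`, with four matching min/max slots inside the PROC MI statement and `nimpute=1` within each BY `_imputation_` group.
- **Tipping-point code:** use `var trt01pn base y1 y2 y3;`.
- **SAP 8.3.3.3.1 and 8.3.3.3.2:** state in one sentence each that the baseline Coding score is in the imputation model.

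The cost is a few code lines and two sentences, with no new data. Where baseline adds nothing (decaying correlation, Day 14 present), including it cost at most about 1.5% in SE. It removes most of the difference from the MMRM at zero shift, but not all, because sequential regression matches the MMRM only approximately.

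A separate item in the same block, not evidence for this point: the tipping-point code has "mnar adjust( y1 y2 y3 / shift=&sj adjustobs=(trt01pn='1') ); *active treatment is used", whereas control-based Step 3 labels '1' as control and SAP 8.3.3.3.2 shifts the SAGE-718 group. These must be reconciled. The zero-shift figures do not depend on this, because at zero shift nothing is moved.

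### The sample code for the control-based imputation has no filter before pooling: once its other errors are repaired, the Day 42 group would mix five contrasts, only one of which is SAGE-718 versus placebo at Day 42

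*SAP*

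**What the plan says.** SAP Section 8.3.3.3.1 plans a control-based pattern-mixture multiple imputation if at least 10% of participants lack the primary endpoint. Each completed data set is analysed with the MMRM, and the results "are combined to produce inferential results". Section 8.3.3.1 names the comparison of interest: SAGE-718 against placebo at Day 42.

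Appendix B gives sample code. The post-baseline visits are "y1=Day 14, y2=Day 42, y3=Day 70". Step 5 requests "lsmeans trt01pn*avisitn / diff=all cl alpha=0.05" and saves the output with "ods output lsmeans=lsmeans diff=diffs". Step 6 pools twice:

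- The LS means are pooled "by treatment avisit", so each arm and visit is kept apart.
- The differences are sorted "by avisit _imputatoin" (with a trailing underscore in the SAP) and passed to "proc mianalyze parms=diffs", grouped by visit label only.

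Between Step 5 and the second pooling call, no statement drops within-arm or cross-visit differences.

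**The concern.** Rubin's rules assume that every row in a group estimates the same quantity, once per imputed data set. Here one visit label covers several different quantities. Averaging them gives a number that is not the planned treatment difference, and real differences between the contrasts are counted as imputation uncertainty.

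The analysis feeds a named deliverable, Table 14.2.1.2.1. It is likely to be triggered, since Section 5.2 anticipates 20% dropout against a 10% threshold. The tipping-point analysis in Section 8.3.3.3.2 runs only after a significant primary result, so this is the one planned missing-not-at-random analysis that does not depend on significance. An artefact here would misstate how robust the trial is to missing data.

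**Working it through.** **Plan's own figures.** The SAP gives no number for Step 6. Its design figures, used below as the scenario, reproduce: 0.8/1.07 = 0.748, stated as 0.75; two-sample t-test power at 30 per arm is 81.5%, stated as 80%; 30/0.8 = 37.5, rounded up to 38 per arm, or 76 in total.

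**Row count.** Two arms by three visits give 6 cells and 6 × 5/2 = 15 differences. Write A for SAGE-718 and P for placebo. The CLASS statement "class subjid trt01pn(ref='1') avisitn" sets level 1 as reference, and the imputation code treats level 1 as control, so P is ordered last. Grouped by the visit of the first cell:

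| Visit label | Rows per imputation | Wanted rows |
|---|---|---|
| Day 14 | 5 + 2 = 7 | 1 |
| Day 42 | 4 + 1 = 5 | 1 |
| Day 70 | 3 + 0 = 3 | 1 |

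The Day 42 rows are A42−A70, A42−P14, A42−P42, A42−P70 and P42−P70.

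**What the Day 42 average estimates.** Summing the five and dividing by 5 gives (4·A42 − A70 − P14 − 2·P70)/5. P42 enters once with each sign and cancels. If the reference arm were ordered first, the roles would swap: A42 would cancel and the sign would reverse.

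**Size under a simple assumption.** Let the effect be a constant d and the placebo change flat at zero. The five contrasts are d−d = 0, d, d, d and 0.

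- Mean: 3d/5 = 0.6d. For d = 0.75 this is 0.45.
- Variance between contrasts: 0.6d² − (0.6d)² = 0.24d²; SD 0.49d.
- If each of the k = 5m rows counts as an imputation, the between-imputation term (1 + 1/k)·B is at least 0.24d²·(5m+1)/(5m−1). The SE cannot be smaller than its square root.
- Upper limit of estimate/SE: 0.6/√(0.24·26/24) = 1.18 at m = 5; 0.6/√(0.24·101/99) = 1.21 at m = 20; 0.6/√(0.24·501/499) = 1.22 at m = 100. The SAP mentions a range for m of 5 to 100.

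The limit is free of d and of the sample size. It describes the contrasts at their assumed means; sampling error moves individual trials around it. It lies well below 1.96.

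**Simulation, illustrative only.** Assumptions: 38 per arm; 20% dropout, four-fifths of it before Day 42 (so about 16% missing at Day 42); change SD 1; correlation between visits 0.7; imputation from the placebo model; m = 20; 400 trials per profile.

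| Profile (Days 14/42/70) | Wanted row: estimate, SE, p<0.05 | All Day 42 rows: estimate, SE, p<0.05 |
|---|---|---|
| Effect 0.75 throughout, flat placebo | 0.68, 0.23, 87% | 0.42, 0.41, 0% |
| Effect 0.375/0.75/0, flat placebo | 0.65, 0.23, 83% | 0.52, 0.36, 7% |
| Effect 0.75 throughout, placebo gains 0.2/0.4/0.6 | 0.68, 0.23, 86% | 0.34, 0.51, 0% |
| No effect, placebo gains 0.2/0.4/0.6 | 0.00, 0.23, 2.5% | −0.09, 0.30, 0% |

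The wanted row falls below 0.75 because control-based imputation itself pulls the effect towards placebo. That is intended and is not part of this point.

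**The case against.** A reader might infer that the sponsor's pooled Day 42 estimate and p-value are wrong as the code stands. The documents do not support that. The printed code would probably stop first. Step 6 groups by `avisit` and `treatment`, whereas the Step 5 model uses `trt01pn` and `avisitn`. The imputation index is misspelled. `PARMS=` with `modeleffects estimate` does not suit a data set of differences. The material is headed as sample code, Steps 4-1 and 4-2 are bare descriptions, and the seed and m are placeholders, so some data handling may simply not be printed. The prose names the right comparison, and nowhere does the SAP plan to pool cross-visit contrasts.

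There are also safeguards. The LS means are pooled by arm and visit, so once the names are repaired their Day 42 difference should expose a mismatch. Section 8.3.3.3 commits the sponsor to explain a sensitivity result in a different direction.

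Much of this stands, and it limits the point to what would happen after a partial repair. It does not remove it. Errors that halt a program get fixed; a missing filter does not halt anything, and a second programmer working from the same text could repeat it. The SAP does not require the cross-check against the pooled means. The Section 8.3.3.3 commitment is tied to direction, and in the simulated profiles with a true effect the unfiltered estimate keeps its direction while shrinking and losing precision.

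**Conclusion.** The omission is real, and its effect is conditional: it bites if the halting errors are corrected and no restriction is added. Then only 1 of 5 Day 42 rows per imputation is the wanted contrast, and placebo at Day 42 drops out of the average. These facts rest only on the three visits, two arms and the reference arm being ordered last.

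The size depends on the time course. Under a constant effect and flat placebo, the estimate is 0.6 of the truth and estimate/SE is capped near 1.2. The simulated rates show direction and should not be read as predictions for this trial.

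A reader might also extend the point to the primary analysis. That does not follow: the primary MMRM code requests the same differences but pools nothing, so the correct row can be read off directly. The exposure is one sensitivity table that could wrongly appear to contradict a positive primary result. It should be fixed, but it does not threaten the primary result.

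**What to change.** Before the second pooling call in Step 6, keep only rows of `diffs` with `avisitn=_avisitn` and `trt01pn ne _trt01pn`, leaving one row per visit and imputation. Fix the sign as SAGE-718 minus placebo. Pool with `data=diffs`, `modeleffects estimate; stderr stderr;`, by `avisitn`. Alternatively, replace the all-pairs request in Step 5 by one ESTIMATE statement per visit.

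In the same edit, align the arm, visit and subject variable names across Steps 5 and 6 and correct the imputation index. Confirm which arm is level 1: the imputation code labels it control, while a comment in the tipping-point code labels it active. As a check, the pooled Day 42 difference should equal the difference of the two pooled Day 42 LS means.

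The cost is a few lines of code and a small Appendix B revision before database lock, with no change to data, design or the primary analysis.
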